1.1 Background

Since December 2019, coronavirus disease 2019 (COVID-19) caused by severe acute respiratory syndrome coronavirus 2 (SARS-CoV-2) infection has spread around the world and become a global pandemic. COVID-19 affects the health and social and economic life of millions of people. Especially the elderly and persons with preexisting conditions (e.g. asthma, diabetes, and heart disease) have an increased risk of a severe and potentially lethal course of the disease. With the nucleoside-modified RNA (modRNA) vaccine BNT162b2 (BioNTech SE/Pfizer), the first vaccine gained market authorization (e.g. in the UK, US, and EU) (Polack, Thomas et al. 2020). Similarly, mRNA-1273 (Moderna) has gained regulatory approval as SARS-CoV-2 vaccine, e.g. in UK, US, and EU. Most recently, Astra Zeneca's vaccine received approval in the UK. More approvals for these and other vaccines around the world are expected for 2021.

Multiple sclerosis (MS) is an autoimmune disease which causes demyelination and neuronal damage in the central nervous system. Worldwide, approximately 2.5 million people are affected by MS, most patients presenting with relapsing forms (RMS).

Between 2016 and 2019, two phase III clinical trials (ASCLEPIOS I & II) showed that monthly subcutaneous injections of ofatumumab can reduce the annual relapse rate and probability of confirmed disability progression compared to teriflunomide (Hauser, Bar-Or et al. 2020). Ofatumumab is a fully human anti-CD20 monoclonal antibody that selectively depletes CD20+ B- and T-cells, which prevent migration to the CNS and the formation of inflammatory lesions. Since August 2020, ofatumumab (Kesimpta) is available as treatment for RMS patients in the US and EMA approval is expected by Q2 2021.

A major concern about B-cell depleting therapies in the context of vaccination is the potentially reduced immune response to vaccines as seen e.g. in the VELOCE trial assessing the immune response in patients treated with the anti-CD20 monoclonal antibody ocrelizumab (Bar-Or, Calkwood et al. 2020). However, the average serum IgG levels in the ASCLEPIOS I and II trials remained well within the reference range over time and no association was observed between a decrease in immunoglobulin levels and the incidence of serious/non-serious infections in ofatumumab-treated patients (Wiendl 2020).

Although B-cells have been assumed to be the major drivers for establishment of immunity after vaccination, it has recently been shown that T-cells might be equally important for vaccine-induced immunity especially against intracellular infections like viruses (Ahmed and Akondy 2011). It has been observed for previous coronavirus-caused disease that T-cell responses were better markers for prior coronavirus infections than antibodies as some COVID-19 patients (especially with mild disease) don't undergo seroconversion and T-cell responses can be detected for a longer time period (Hellerstein 2020). Immunological memory to SARS-CoV-2 has been recently demonstrated for 8 months post infection (Dan, Mateus et al. 2021).

Concomitant with these findings, it has been shown that 100% of all COVID-19 patients showed specific CD4⁺ and 70% showed specific CD8⁺ T-cell responses (Grifoni, Weiskopf et al. 2020). Furthermore, it was observed that upon contact with a confirmed COVID-19 patient, multiple persons developed disease symptoms and a T-cell mediated response without

seroconversion suggesting the importance of T-cell activation even in the absence of SARS-CoV-2 neutralizing antibodies (Gallais, Velay et al. 2020).

When looking into the immune responses after vaccination with the two newly approved mRNA vaccines it was shown that both, BNT162b2 (Pfizer/BioNTech) and mRNA-1273 (Moderna), not only induced an antibody-response against the SARS-CoV-2 spike protein but also functional CD4⁺ and CD8⁺ T-cell responses (Jackson, Anderson et al. 2020, Sahin, Muik et al. 2020).

Especially in the context of ofatumumab treatment and the imminent B-cell depletion, the activation of CD4⁺ and CD8⁺ T-cells plays an even more important role for the development of vaccine-induced immunity. It is therefore essential to understand the impact of concomitant ofatumumab treatment on

- 1) the cellular response, investigating the development of CD4⁺ and CD8⁺ T cell responses against the SARS-CoV-2 spike protein, which is necessary for infection of the target cell (Huang, Yang et al. 2020), and
- 2) the humoral immune response, investigating SARS-CoV-2 serum neutralizing antibody levels.

In recent publications describing SARS-CoV-2 mRNA vaccines, functional T-cell responses were defined as interferon γ (IFN γ) secretion by T-cells measured by enzyme-linked immuno spot (ELISpot) assay after *in vitro* stimulation with a peptide mix resembling the SARS-CoV-2 spike protein (Jackson, Anderson et al. 2020, Sahin, Muik et al. 2020). In this study, we will perform ELISpot assays followed by detailed immunophenotyping to further characterize the developed T-cell response. Furthermore, we will test for functional antibodies, i.e. antibodies that inhibit the binding of the viral spike protein to the human angiotensin-converting enzyme 2 (ACE2) receptor, which is the first and necessarily required step during SARS-CoV-2 infection (Yang et al. 2020). The detection of SARS-CoV-2 serum functional antibodies after vaccination in patients negative for this parameter at baseline is defined as seroconversion according to World Health Organization guidelines (WHO guideline, 2020).

In this study, immune response to SARS-CoV-2 mRNA vaccines will be analyzed in patients receiving the vaccine before starting ofatumumab treatment (cohort 1) or during stable ofatumumab treatment (cohort 2).

If suggested by local regulations, patients will be allowed to receive additional SARS-CoV-2 vaccines (either as additional booster or yearly refresher) during the study according to the physician's discretion and as part of the clinical routine.

Data gathered within AMA-VACC (CBAF312ADE03) will serve to describe differences to other DMTs. In AMA-VACC, humoral and cellular immune response is assessed at identical timepoints as within this study in MS patients treated with siponimod, platform therapies (i.e. interferons, glatiramer acetate, teriflunomide, dimethyl fumarate), or currently without DMT.

1.2 Purpose

B-cell depleting therapies have in the past been shown to impair the immune response to conventional vaccines. The objective of this study is to assess whether participants treated with monthly s.c. injections of ofatumumab (20 mg) can mount an adequate immune response to the new class of SARS-CoV-2 modRNA vaccines (initial or booster) as measured by humoral and cellular responses. The study will further investigate the maintenance of SARS-CoV-2 specific responses for up to 18 months after the initial vaccination.

2 Objectives and endpoints

Table 2-1 Objectives and related endpoints

Objective(s)	Endpoint(s)
Primary Objective(s) 
 To estimate the proportion of RMS patients having established SARS-CoV-2-specific T cells after receiving a modRNA vaccine (initial vaccination or booster) either before or after starting ofatumumab treatment. 	Endpoint(s) for primary objective(s) 
 Proportion of RMS patients having established SARS-CoV-2-specific T cells as defined by detection of SARS-CoV-2 reactive T-cells, measured by e.g. enzyme-linked immunosorbent spot (ELIspot) assay from T-cells that were stimulated with SARS-CoV-2 peptide mix, either one month after second dose of vaccine or one month after booster vaccine in participants who received the respective vaccine before or after starting ofatumumab treatment (yes/no)
Secondary Objective(s) 
 To estimate the proportion of RMS patients maintaining for up to 18 months SARS-CoV-2-specific T cells after receiving a modRNA vaccine either before or after starting ofatumumab treatment. To estimate the increase in specific T-cells after receiving a modRNA booster vaccine either before or after starting ofatumumab treatment. 	Endpoint(s) for secondary objective(s) 
 Proportion of RMS patients with detectable SARS-CoV-2 reactive T-cells one week, 6, 12 and 18 months after second dose of vaccine or 6 and 12 months after booster vaccine in participants who received the vaccine before or after starting ofatumumab treatment (yes/no) Fold change of SARS-CoV-2 specific T-cell levels one week, 1 month, 6 months, 12 months and 18 months after the second dose of vaccine or 1 months, 6 months and 18 months after a booster vaccine compared to the last timepoint before the respective vaccine

Objective(s)	Endpoint(s)

• To estimate the proportion of RMS patients achieving seroconversion (i.e. having SARS-CoV-2 serum neutralizing antibodies) after receiving a modRNA vaccine either before or after starting ofatumumab treatment.• To estimate the proportion of RMS patients maintaining for up to 18 months quantifiable levels of SARS-CoV-2 serum functional antibodies after receiving a modRNA vaccine either before or after starting ofatumumab treatment.• Describing phenotypically the cellular response after receiving a modRNA vaccine either before or after starting ofatumumab treatment.• Describing safety and tolerability, incl. patients developing coronavirus disease 2019 (COVID-19)	
• Proportion of RMS patients achieving seroconversion (i.e. having SARS-CoV-2 serum neutralizing antibodies) after receiving a modRNA vaccine either before or after starting ofatumumab treatment (yes/no)• Proportion of RMS patients with quantifiable levels of SARS-CoV-2 serum functional antibodies one week, 1, 6, 12 and 18 months after receiving the second dose of modRNA vaccine or 1, 6 and 12 months after a booster shot either before or after starting ofatumumab treatment (yes/no)• Phenotypical characterization of peripheral blood mononuclear cells for CD45, CD3, CD4, CD8, CD62L, CD45RA, CD45R0, CCR7• Immunophenotyping for naive, central memory, effector memory, and effector cells on CD4⁺ and CD8⁺ cells• Measuring cells positive for intracellular cytokine-staining for interferon-gamma and interleukin-4• AEs, SAEs, incl. patients with clinical confirmed COVID-19

Objective(s)	Endpoint(s)

2.1 Primary estimands

The primary clinical question of interest is: What is the proportion of RMS patients having developed a specific immune response after receiving a SARS-CoV-2 mRNA vaccine (initial vaccination or booster vaccine) either before or after starting ofatumumab treatment.

The justification for the primary estimand is that it will capture whether ofatumumab-treated patients will mount a specific T-cell response after receiving a SARS-CoV-2 mRNA vaccine assessed by enzyme-linked immunosorbent spot (ELISpot) assays from T-cells that were stimulated with SARS-CoV-2 peptide mix.

Patients will receive either their initial vaccination (1st and 2nd SARS-CoV-2 vaccines) or a booster vaccine before or after starting ofatumumab treatment. In both cases we want to assess if ofatumumab initiation negatively affects or prevents the immune response.

Since this is not a randomized trial, no randomization needs to be preserved and the ITT-principle and the associated estimands framework do not apply. However, this protocol will keep as close as appropriate to the terminology and the definitions established within that framework.

The primary estimand is described by the following attributes:

1. **Population:** Patients with relapsing MS (RMS) divided in two cohorts, each receiving a SARS-CoV-2 mRNA vaccine as part of clinical routine: (1) vaccination before start of ofatumumab treatment, (2) vaccination after having been on stable ofatumumab treatment for at least 4 weeks. The SARS-CoV-2 mRNA vaccine can be either the initial vaccination cycle (for patient that are exposed to the vaccine for the first time; cohort 1a and cohort 2a) or a booster vaccination (for patients that have already completed the initial vaccination cycle; cohort 1b and cohort 2b). Patients in cohort 1a or 2a who fail to receive

their second dose of vaccine for whatever reason will be included in the analysis as non-responders. Patients in cohort 1a and 2a who did receive their second dose of vaccine and patients in cohort 1b and 2b who received their booster shot and do not have a valid determination of specific T-cell response to SARS-CoV-2 for whatever reason will be excluded from the analysis of vaccine efficacy.

2. **Variable:** Receiving the second dose of mRNA vaccine (for cohort 1a and 2a) or a booster vaccination (cohort 1b and 2b) and mounting a specific T cell response one month after second dose of vaccine (cohort 1a and 2a) or booster vaccine (cohort 1b and 2b) defined by detection of SARS-CoV-2 specific T-cells by ELISpot assays after stimulation of T-cells with SARS-CoV-2 peptide mix (yes/no)
3. **Treatment of interest:** ofatumumab treatment, which is started either before or after receiving a SARS-CoV-2 mRNA vaccine (initial vaccination cycle or booster vaccine)
4. **Intercurrent events:**
 - a. Vaccination with a non-mRNA vaccine: patients will be excluded from the study
 - b. Failure to receive the second dose of vaccine (for cohort 1a and 2a): patients will be classified as non-responders
 - c. Failure to initiate ofatumumab treatment within six weeks after completion of the vaccination cycle (cohort 1a) or of the booster vaccine (cohort 1b): patients will be excluded from the efficacy analyses
 - d. Failure to complete ofatumumab initiation or interruption of ofatumumab treatment prior to first vaccination (cohort 2a) or prior to booster vaccination (cohort 2b): patients will be excluded from the study
 - e. No valid detection of SARS-CoV-2 specific T-cells: patients will be excluded from the efficacy analyses if they received their second dose of vaccine (cohort 1a and 2a) or booster vaccine (cohort 1b and 2b) and further analyses will be performed to confirm methodical reasons
5. **Summary measure:** n.a., there will be no formal comparison between cohorts. Response rates will only be calculated within each cohort.

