12.1 Analysis sets

For all analysis sets, participants will be analyzed according to the study treatment(s) received.

The safety analysis set will include all participants that received any study drug.

The efficacy analysis sets at one week, one month, six months, 12 months and 18 months after the second SARS-CoV-2 vaccine and 1, 6 and 12 months after a booster vaccine, respectively, will include all participants who have a valid determination of SARS-CoV-2 reactive T-cells at that time point plus those who failed to receive their second dose of vaccine for whatever reason. The latter will be counted as non-responders. Patients completing vaccination but fail to provide a blood sample at one week after the second vaccination will be excluded from the study and analysis.

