12.4.4 Supportive analyses

Patient demographics and baseline characteristics among both cohorts will be compared in the data analysis. Additionally, patients receiving their initial vaccination (cohorts 1a and 2a) vs. a booster shot (cohort 1b and 2b) will be analyzed separately. If patients received a non-mRNA vaccine as booster, this would be reflected in the analysis.

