2.2 Analysis sets

For all analysis sets, participants will be analyzed according to the study treatment received.

The Safety Analysis Set (SAF) will include all participants that received any study drug.

The Efficacy Analysis Set (EAS) will include all patients of the Safety Set who received a mRNA vaccine. Patients who failed their second dose of mRNA vaccine are included in the Efficacy Analysis Set, but counted as non-responders. Patients with invalid or missing efficacy parameter at a respective time point are included in the EAS, but excluded from the denominator for that time point when calculating responder-rates.

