2.5.3 Handling of missing values/censoring/discontinuations

Cohort 1a and cohort 2a: Patients who fail to receive their first dose of vaccine for whatever reason are excluded from the efficacy analysis Set(s). The number of these patients is displayed in the patient disposition table.

Patients who fail to receive their second dose of vaccine for whatever reason will be included in the analysis as non-responders. The number of these patients is displayed in the analysis table.

Patients who did receive their second dose of vaccine and do not have a valid determination of reactive T-cells to SARS-CoV-2 for whatever reason will be excluded from the analysis of vaccine efficacy at the respective time point. The number of these patients is displayed in the analysis table.

Cohort 1b and cohort 2b: Patients who fail to receive their booster vaccination for whatever reason are excluded from the efficacy analysis Sets(s). The number of these patients is displayed in the patient disposition table.

Patients who did receive their booster vaccination and do not have a valid determination of reactive T-cells to SARS-CoV-2 for whatever reason will be excluded from the analysis of vaccine efficacy at the respective time point. The number of these patients is displayed in the analysis table.

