5.4 Rule of exclusion criteria of analysis sets

Deviation ID	Description of Deviation	Exclusion in Analyses
I01	Incl. crit. no. 1 (IFC) violated	Excluded from all analysis Sets
S02	Different vaccines at first and 2 nd vaccination	Excluded from Efficacy Analysis Set

Table 2 Subject Classification

Analysis Set	PD ID that cause subjects to be excluded	Non-PD criteria that cause subjects to be excluded
SAF/Efficacy Analysis Set	NA	Not having any study treatment
Efficacy Analysis Set	NA	No mRNA vaccine administered: - Patients of cohort 1a and 2a who missed the 1 st vaccination - Patients of cohort 1b and 2b who missed the (study) booster vaccination

6 Reference

None.

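### Intercurrent event a removes from the study any patient given a non-mRNA vaccine; for boosters this conflicts with Protocol 12.4.4 and 12.1 and with SAP 2.2 and 5.4

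*Protocol*

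**What the plan says.** Protocol 2.1 lists the intercurrent events of the primary estimand. Event a is "Vaccination with a non-mRNA vaccine: patients will be excluded from the study", and SAP 2.5.1 repeats it word for word. It is the only event in the list that names no cohort, dose or time. Event c, in the same list, uses a narrower consequence: "or of the booster vaccine (cohort 1b): patients will be excluded from the efficacy analyses". The estimand population is patients "each receiving a SARS-CoV-2 mRNA vaccine as part of clinical routine".

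Other current sections bear on the same patients:

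- Protocol 12.4.4: "If patients received a non-mRNA vaccine as booster, this would be reflected in the analysis".
- Protocol 12.1: the efficacy set at each time point "will include all participants who have a valid determination of SARS-CoV-2 reactive T-cells at that time point", plus patients without a second dose, who count as non-responders. It sets no condition on vaccine type.
- Protocol 6.2.2 prohibits non-mRNA vaccines but attaches no removal from the study. Under 9.1.1, prohibited treatment stops study treatment, and a participant who stops study treatment is not regarded as withdrawn unless consent is withdrawn.
- SAP 2.2: "The Efficacy Analysis Set (EAS) will include all patients of the Safety Set who received a mRNA vaccine".
- SAP 2.5.3, for cohorts 1b and 2b: "Patients who fail to receive their booster vaccination for whatever reason are excluded from the efficacy analysis". It is silent on the type of booster.
- SAP 5.4 removes from the efficacy set patients with different vaccines at doses 1 and 2 (rule S02) and patients under the heading "No mRNA vaccine administered". The 1b/2b bullet below that heading names only a missed study booster.

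**The concern.** Boosters are allowed throughout follow-up in all cohorts and are given outside the study, and Protocol 12.4.4 itself foresees that one might be non-mRNA. Take a cohort 1a or 2a patient with two mRNA doses, a usable month-1 result and, some months later, a non-mRNA booster. An analyst who follows event a removes the patient, including a primary result obtained before the event. An analyst who follows Protocol 12.1 or SAP 2.2 keeps the patient. The same split arises for a 1b or 2b patient with an mRNA study booster and a later non-mRNA booster.

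The SAP therefore contains two rules for one patient (2.5.1 against 2.2 and 5.4). SAP section 4, where departures from the protocol are declared, does not say which prevails. At stake are the denominators of the month-1 rate and of the later time-point rates.

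**Working it through.** **Step 1: the texts side by side**

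| Situation | Event a (Protocol 2.1, SAP 2.5.1) | Other current text | Conflict? |
|---|---|---|---|
| 1a/2a: non-mRNA vaccine at dose 1 or 2 | Removed from the study | SAP 5.4 (S02, or the no-mRNA rule) removes from the efficacy set; 12.4.4 does not apply because it covers boosters only | Largely agree on the rates. One loose end: for a non-mRNA dose 2 after an mRNA dose 1, SAP 2.2 could instead count the patient as a non-responder |
| 1b/2b: study booster itself non-mRNA | Removed from the study | Population definition and SAP 5.4 heading point to leaving the patient out of the primary rate; 12.4.4 wants the booster reflected; the 5.4 bullet covers only a missed booster | Direction mostly clear; bullet narrower than its heading |
| 1a/2a: non-mRNA booster after the mRNA course | Removed from the study | Kept by Protocol 12.1 and SAP 2.2; no SAP 5.4 exclusion met; 12.4.4 reflects it | Yes |
| 1b/2b: later non-mRNA booster after an mRNA study booster | Removed from the study | As in the row above | Yes |

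A non-mRNA vaccine before the study is a matter for exclusion criterion 8, not for event a.

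**Step 2: the plan's own precision figure**

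Inputs from Protocol 12.8.1 and SAP section 3: n = 20 per arm and response rates of 70%, 75% and 80%. The half-width of a 95% interval by the normal approximation is 1.96 × √(p(1 − p)/20):

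- p = 0.70: 20.08 points (stated 20.1)
- p = 0.75: 18.98 points (stated 19)
- p = 0.80: 17.53 points (stated 17.5)

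The stated figures are reproduced and serve as the yardstick.

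**Step 3: what dropping k patients does to the rate**

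The documents do not give k; k = 1 and k = 2 are assumptions for scale. With x responders among 20, of whom r are among the k patients dropped, the rate changes from x/20 to (x − r)/(20 − k).

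| Kept | k = 1, responder dropped | k = 1, non-responder dropped | k = 2, both responders | k = 2, one of each | k = 2, both non-responders |
|---|---|---|---|---|---|
| 14/20 = 70.0% | 13/19 = 68.4% (-1.6) | 14/19 = 73.7% (+3.7) | 12/18 = 66.7% (-3.3) | 13/18 = 72.2% (+2.2) | 14/18 = 77.8% (+7.8) |
| 15/20 = 75.0% | 14/19 = 73.7% (-1.3) | 15/19 = 78.9% (+3.9) | 13/18 = 72.2% (-2.8) | 14/18 = 77.8% (+2.8) | 15/18 = 83.3% (+8.3) |
| 16/20 = 80.0% | 15/19 = 78.9% (-1.1) | 16/19 = 84.2% (+4.2) | 14/18 = 77.8% (-2.2) | 15/18 = 83.3% (+3.3) | 16/18 = 88.9% (+8.9) |

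The largest shift is +8.9 points, from 16/20 (Clopper-Pearson 95% interval 56.3 to 94.3%) to 16/18 (65.3 to 98.6%). Every shift is smaller than the planned half-width. With k = 0 there is no effect.

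**The case against.** The strongest reply is that event a belongs to the primary estimand and should be read within it. The glossary limits intercurrent events to those that affect the measurements behind the clinical question, and a booster after the month-1 sample cannot affect that sample. Event d also removes patients from the study and concerns only what happens before vaccination. On that reading event a touches only the doses that define the primary time point. The reading is possible, but the text does not state it. The list separates removal from the study from removal from the efficacy analyses, and event a uses the wider consequence without a qualifier. The clash with 12.4.4 remains.

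Two further replies stand in part. Reflecting a booster in the analysis is vague wording under a supportive heading, and separate reporting would satisfy it; still, a patient removed from the study is not naturally reflected in its analysis. And Protocol 12.1 and SAP 2.2 and 5.4 also omit the removals in events c and d, so their silence alone is weak evidence. They do, however, positively admit the patient described.

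Two stronger readings are tempting and not supported. A reader might infer that event a is contradicted for every dose. It is not: 12.4.4 covers boosters only, and for doses 1 and 2 SAP 5.4 largely agrees with event a. A reader might also infer that all later follow-up of such a patient is lost. Protocol 9.1.1 does not treat these patients as withdrawn and asks them to return for assessments where possible.

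**Conclusion.** The point holds for boosters and is minor. Event a as written is wider than Protocol 12.4.4, Protocol 12.1 and SAP 2.2 and 5.4 allow, and Protocol 6.2.2 and 9.1.1 do not withdraw such patients either. The conflict lies between current sections and does not rest on the amendment summaries. Its practical consequence is that a month-1 result obtained before a non-mRNA booster may or may not be counted, depending on which section the analyst follows.

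The size is small and hypothetical. Under the assumption of one or two affected patients among 20, the rate moves by at most 8.9 points, inside the planned 17.5 to 20.1. All analyses are descriptive, so no test is affected. A reader might infer that the reported rates are biased; the documents record no affected patient, so that cannot be said.

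**What to change.** Narrow event a instead of deleting it, because it is the Protocol's rule for an on-study non-mRNA dose 1 or 2.

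1. Non-mRNA vaccine at dose 1 or 2 (cohorts 1a, 2a), or as the study booster (cohorts 1b, 2b): the patient is left out of the efficacy analyses of the mRNA response, is followed, and is listed separately. State that S02 takes precedence over the non-responder rule of SAP 2.2 when dose 2 is non-mRNA.
2. Non-mRNA booster after the mRNA dose that defines the primary time point: the patient stays in the study and in the efficacy set. All results before that booster count, including month 1. Later samples stay in the time-point rates, as under Protocol 12.1, and those rates are also shown without them.
3. Align the 1b/2b bullet in SAP 5.4 with its heading: study booster missed, or given as a non-mRNA vaccine.

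Make the change in SAP 2.5.1 and 5.4 and record it in SAP section 4. Correct Protocol 2.1 as well if an amendment is still practical. Protocol 14.1 requires sponsor and ethics committee approval, and health authority approval where applicable. The SAP already cites data notes from September and October 2023, so an amendment may come too late; the SAP change alone would settle the denominators. Whether ofatumumab continues after a prohibited vaccine remains governed by Protocol 9.1.1 and is not altered here.

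The cost is a wording change, one analysis flag and one extra row per affected table. No new assessments are needed.
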